## **7.6. Study participation**

Each subject will have their study participation documented, including the number of cycles completed, the duration of the Follow-up Period, and if discontinuing from the study, the reason

for discontinuation. At the end of each cycle, the subject continuation status for each subject will be documented on the CRF.

If for any reason, either study treatment or observations were discontinued, the reason will be recorded. The primary reasons for discontinuation will be documented:

- Adverse event(s)
- Protocol violation or deviation
- Disease progression
- Subject withdrew consent
- Subject is lost to follow-up
- Death
- Other unspecific reasons

## **8. EVALUATION OF SAFETY, IMMUNOGENICITY AND EFFICACY**

### **8.1. Evaluation of safety and tolerability**

The primary objective of this study intends to evaluate the safety and tolerability of IP. The following evaluations will be performed to measure the safety and tolerability:

Clinical laboratory tests (blood, urine sampling for clinical laboratory parameters), ECOG performance status, physical examinations including vital sign measurements, ECG, and the incidence and severity of treatment-emergent adverse events.

### **8.2. Immunogenicity**

Immunogenicity refers to the development of an immune response to the HLX06 itself, and is characterized by the antibodies (ADA) that the patients may develop to react with HLX06. These may result in more rapid clearance of the IP from the bloodstream or predispose the patient to infusion reactions upon retreatment with IP at a later date. The ADA may also likely potentiate the drug effect by prolonging its half-life. Blood samples for immunogenicity analysis are mandatory and will be collected from all patients prior to every infusion of IP in Cycle 1 and before first infusion in subsequent 5 cycles or up to 18 weeks, whichever comes first and on the day of follow-up visit 1.

### **8.3. Efficacy evaluation**

The efficacy parameters are the disease control rate (number of patients with CR/PR/SD divided by the total number of patients treated), and objective response rate (ORR) (number of patients with confirmed responses of CR or PR, divided by the total number of treated patients with measurable disease at baseline). Tumor response status will be assessed using RECIST 1

The response to treatment will be assessed in the following schedule:

1. For the first 24 weeks, treatment evaluation is conducted every 8 weeks (regardless of treatment delay).
2. After 24 weeks, treatment evaluation is conducted every 12 weeks

Tumor specific antigen levels (i.e. CEA, CA125, CA19-9, AFP, PSA for prostate cancer) are not used to confirm response, but they will be measured to provide ancillary support for disease response when appropriate in some tumor types.

Efficacy evaluation should use the same modalities. Repeat bone scan for metastatic bone disease is indicated based on clinical judgement by the Investigator.

## **9. PHARMACOKINETIC AND PHARMACODYNAMIC EVALUATIONS**

### **9.1. Pharmacokinetic studies**

Pharmacokinetic study is mandatory for all patients in this study. Blood samples should be drawn from a site other than the infusion site (i.e., contralateral arm) on days of infusion. If the infusion was interrupted, the reason for interruption will also be documented on the CRF.

For pharmacokinetic analysis of HLX06, blood samples of 5 mL were drawn pre-dose (within one hour before first infusion), after the end of infusion (within 30 minutes) and at 2, 4, 8 ( $\pm 15$  minutes allowable) hours as well as at 24, 48, 96, and 168 hours after the end of 1st and 4th infusion in Cycle 1. Additional time points include pre-dose and after the end of 2nd and 3rd infusions (within 30 minutes) in Cycle 1. Thereafter, the serum levels of HLX06 will be measured before the first infusion of Cycle 2 to Cycle 6 or up to 24 weeks, whichever comes first; and on the day of follow-up visit 1, whenever possible.

Blood samples will be processed to collect serum and stored at -70 degrees Celsius. Serum samples will be analyzed for HLX06 by a validated ELISA method.

Non-compartmental pharmacokinetic analysis will be used to estimate the PK parameters. The following parameters are determined from the serum concentration data of HLX06: maximum serum concentration ( $C_{max}$ ), time to reach  $C_{max}$  ( $T_{max}$ ), elimination rate constant ( $\lambda_z$ ), elimination half-life ( $t_{1/2}$ ), area under the serum concentration-versus-time curve within one dosing interval ( $AUC_{0-\tau_{au}}$ ), area under the serum concentration-versus-time curve until infinity ( $AUC_{0-\infty}$ ), volume of distribution during terminal phase ( $V_z$ ), and at steady state ( $V_{ss}$ ), total body clearance from serum CL, and mean residence time (MRT).  $C_{max}$ , and  $T_{max}$  are taken directly from the plasma concentration curve, terminal half-life is determined from the terminal slope of the log-transformed plasma concentration curve using linear regression on terminal data points of the curve.

Concentrations below the lower limit of quantification, which are before the last quantifiable data point, are taken as zero for calculating the AUC. Pharmacokinetic results are presented only descriptively. No statistical tests are performed with pharmacokinetic parameters.

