### **Pre-medications**

Primary prophylaxis for first infusion reaction of HLX06 is NOT mandatory. If the patients experience infusion reactions, allergic reactions, nausea, vomiting or other symptoms/signs related to infusion of experimental drugs, pre-medications to mitigate these reactions with antihistamine, acetaminophen, corticosteroid or 5-HT3 antagonist or by institutional guidelines are permitted in subsequent infusions. Infusion time is two hours.

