### **Pharmacokinetic studies**

To measure the serum concentration of HLX06, blood samples will be collected pre-dose (within one hour), immediately after infusion (within 30 minutes), and at 2, 4, 8, 24, 48, 96, and 168 hours from the 1st and 4th infusion in cycle 1.

Additional time points include pre-dose and after 2nd and 3rd infusions (30 minutes allowable) in cycle 1. Thereafter, the blood levels of HLX06 will be measured before the first infusion of cycle 2 to cycle 6 or up to 24 weeks, whichever comes first; on the 28-day follow-up visit, whenever possible.

Non-compartmental pharmacokinetic analysis will be used to estimate the PK parameters.

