#### **5.6. Preparation of investigational product and administration**

HLX06 is intended for **intravenous** injection only with final concentration no more than 10 mg/mL

To minimize the error in the adjustment of infusion rate, HLX06 is constituted to the final volume of **200 mL** with normal saline and infused intravenously in **two hours**, regardless of the assigned dose level. Diluted HLX06, if not used in 4 hours, should be stored at 2-8 °C and be used in 24 hours.

The following procedure is required to prepare the HLX06 solution.

Confirm the dose needed to be infused and calculate the volume needed. Draw up the volume of a vial of HLX06 using a sterile syringe.

Fill HLX06 in a sterile evacuated container or bag such as glass containers, polyolefin bags (ethylene vinyl acetate bags, DEHP plasticized PVC bags, or PVC bags).

Repeat the procedure until the calculated volume has been put in to the container. Use a new needle for each vial.

Dilute the drawn HLX06 with sterile 0.9% saline solution to make the final volume of 200 mL.

Administer through a low protein binding 0.22-micrometer in-line filter (placed as proximal to the patient as practical). Affix the infusion line and prime it with diluted HLX06 before starting the infusion. **Set the infusion rate to 100 mL per hour.**

At the end of infusion period, flush the line with sufficient amount of normal saline.

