#### **7.2.2.3. Procedures for the first infusion in a cycle.**

For preparation of IP and the requirement for infusion set, please refer to Section 5.6.

Treatment will begin with the first intravenous infusion of IP (Day 1) and will continue every 7 days for a total of 4 doses (Days 1, 8, 15 and 22) in a cycle with the response assessment described in Section 8.

The followings are the procedure required before the first infusion in each cycle: (*the laboratory tests before the first infusion may be waived, if the interval between screening tests and first infusion is less than 7 days, and the Investigator judges that the patient's condition remains stationary*).

1. Vital sign measurements to include temperature, pulse, and blood pressure will be obtained as defined in the Section 14.
2. Weight
3. Physical examination (including measurement of vital signs as well as pulmonary, heart, abdomen, and skin assessments with selective neurological examination)
4. ECOG performance status
5. 12-lead ECG
6. Complete blood count (CBC) with differentials, and D-dimer
7. Tumor markers (CEA, CA199, CA125, CA153, alpha-fetoprotein and PSA)
8. Coagulation profile: prothrombin time, partial thromboplastin time, international normalized ratio (PT/PTT/INR).
9. Blood chemistry profile: Fasting glucose, blood urea nitrogen (BUN), creatinine, ALT, AST, total protein, albumin, globulin, alkaline phosphatase, total bilirubin, sodium, potassium, chloride, calcium, magnesium, phosphorus, uric acid, lactate dehydrogenase (LDH), IgG, and IgM
10. Thyroid function tests: thyroid-stimulating hormone (TSH), T3, free thyroxine (FT4)
11. Urinalysis.
12. Urine pregnancy test for female patients with child-bearing potential..
13. Infusions of IP (after all other evaluations for the visit according to the Time and Events Table have been completed except for the post-infusion pharmacokinetic samples)

---

 ECG must be done predose and within 30 minutes after the end of 1st infusion.

 If the tests have been done during the Screening period, no need to repeat the tests before 1st infusion in cycle 1. These should be done every 8 weeks in the first 24 weeks and every 12 weeks thereafter.

For prostate cancer only.

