Immunogenicity study 		X	X	X	X	X								X
Optional PD study 		X	X	X	X									
Imaging procedures														
12-lead ECG 	X	X				X				x				X
Cardiac ultrasound	X													
Chest X-Ray	X													
Tumor assessment CT/MRI imaging	X	Every 8 weeks in the first 24 weeks and every 12 weeks thereafter												X
Brain CT/MRI	X													
Bone scan	X	Repeat bone scan for metastatic bone disease is indicated based on clinical judgement by the Investigator												

 Pharmacokinetic analysis of HLX06: blood samples of 5 mL were drawn within one hour before and at the end of infusion, 2, 4, 8 ( $\pm 15$  minutes allowable) hours as well as at 24, 48, 96, and 168 hours after the start of 1st and 4th infusion in Cycle 1. Additional time points include before and after 2nd and 3rd infusions in Cycle 1. Thereafter, the serum levels of HLX06 will be measured before the first infusion of Cycle 2 to Cycle 6 or up to 24 weeks, whichever comes first; and on the day follow-up visit 1, whenever possible.

 Blood samples for immunogenicity will be collected from all patients prior to every infusion of IP in Cycle 1 and before first infusion in subsequent 5 cycles or up to 18 weeks, whichever comes first; and on the day of follow-up visit 1.

 The sampling time points are predose and after each infusion (within 30 minutes) in cycle 1 in conjunction with pharmacokinetic studies.

 At screening, predose and after the end of 1st infusion (within 30 minutes) of each cycle and on the day of follow-up visit 1.

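### PK sampling times run from the end of infusion in 9.1 but from its start in the schedule; taken literally, 9.1 puts the 168-hour sample after the next dose, and no rule excludes it from the profile

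*Combined protocol and SAP*

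**What the plan says.** Three places give the sampling times for the 1st and 4th infusions of Cycle 1.

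- **Section 9.1** counts from the end of infusion: "hours as well as at 24, 48, 96, and 168 hours after the end of" the 1st and 4th infusion.
- **Section 14, footnote 13** counts from the start: "hours as well as at 24, 48, 96, and 168 hours after the start of 1st and 4th infusion in Cycle 1".
- **Synopsis, Pharmacokinetic studies**, leaves it open: "and at 2, 4, 8, 24, 48, 96, and 168 hours from the 1"st and 4th infusions, without saying which end of the infusion is meant.

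The infusion length is consistent. The synopsis states "Infusion time is two hours", and section 5.6 prepares 200 mL with the instruction "Set the infusion rate to 100 mL per hour". Section 7.2.2.3 gives the interval: treatment "will continue every 7 days for a total of 4 doses (Days 1, 8, 15 and 22) in a cycle".

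Section 9.1 also plans a pre-dose sample before infusions 2 and 3 and before the first infusion of Cycles 2 to 6. It defines AUC0-tau as the "area under the serum concentration-versus-time curve within one dosing interval" and obtains half-life from the log concentrations "using linear regression on terminal data points of the curve". It attaches a ±15-minute tolerance to the 2-, 4- and 8-hour samples and gives none for the 168-hour sample. Nowhere is that sample required to precede the next infusion.

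**The concern.** A site cannot follow both 9.1 and footnote 13, and no text says which governs. The choice matters most for the last sample. Counted from the end of a 2-hour infusion, 168 hours overshoots the weekly interval by exactly the length of the infusion, so the sample meant as a trough becomes a near-peak value of the next dose. Half-life and the extrapolated AUC depend heavily on the last point. AUC0-tau, half-life, CL and Vss are listed secondary endpoints, summarised by cohort. Recording the actual draw time does not help, because the sample contains drug from a second dose.

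The other timed samples also differ by 2 hours between the readings, so sites following different sections would contribute unmatched nominal times to the same cohort summary.

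**Working it through.** **Clock arithmetic (documents only).** Infusion length = 200 mL ÷ 100 mL/h = 2 h, as stated. Dosing interval = 7 × 24 = 168 h. Hours from the start of infusion under each reading:

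| Nominal time | 2 | 4 | 8 | 24 | 48 | 96 | 168 |
|---|---|---|---|---|---|---|---|
| Section 9.1 (from end) | 4 | 6 | 10 | 26 | 50 | 98 | 170 |
| Footnote 13 (from start) | 2 | 4 | 8 | 24 | 48 | 96 | 168 |

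An on-time next infusion runs from 168 to 170 h. The 9.1 sample falls at its end, on Day 8 after infusion 1 and on Cycle 2 Day 1 after infusion 4. Under footnote 13 the 168-hour sample is the next pre-dose sample, but the 2-hour sample coincides with the end-of-infusion sample.

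**Size (illustrative).** The documents give no half-life, so I assume 3 to 14 days. The model has one compartment, dose/volume = 1, T = 2 h and k = ln 2 ÷ half-life. After the end of infusion, C(t) = [(1 − e^(−kT))/(kT)]·e^(−k(t−T)); doses add. AUC is by linear trapezoid, compared with the true AUC from 0 to 168 h.

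Example: half-life 7 days, infusion 1, k = 0.693/168 = 0.00413 per hour.

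- C(98) = 0.670; C(168), pre-dose, = 0.502; C(170) = 0.498 carried over + 0.996 new = 1.494.
- True AUC = (1 − 0.502)/k = 120.7.
- Last segment with the 170-hour point: 72 × (0.670 + 1.494)/2 = 77.9. With the pre-dose point: 70 × (0.670 + 0.502)/2 = 41.0.
- Excess = 36.9, or 36.9/120.7 = 31% of the true AUC.
- The log-linear slope through 50, 98 and 170 h is +0.0055 per hour; the true slope is −0.0041.

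Ratio of computed to true AUC:

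| Assumed half-life (days) | 3 | 5 | 7 | 10 | 14 |
|---|---|---|---|---|---|
| Infusion 1, 170-h value as last point, no pre-dose value | 1.45 | 1.35 | 1.31 | 1.28 | 1.27 |
| Infusion 4, same | 1.36 | 1.22 | 1.17 | 1.13 | 1.11 |
| Infusion 1, pre-dose 168-h value added, 170-h value kept | 1.032 | 1.023 | 1.020 | 1.019 | 1.018 |
| Infusion 1, pre-dose 168-h value, 170-h value dropped | 1.015 | 1.006 | 1.003 | 1.002 | 1.001 |

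In the first two rows the slope over the last three or four points is positive in all ten cases. A bi-exponential model (assumed 40% fast phase with an 18-hour half-life; terminal half-life 3, 5, 8 and 14 days) also gives a positive slope in every case.

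In the one-compartment model, regression on 50, 98 and 168 h (pre-dose) returns the assumed half-life exactly. Adding the pre-dose value while keeping the 170-hour value largely repairs AUC but not the slope: the last three points still rise in every case.

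**The case against.** The strongest reply is that the plan already collects what it needs. The pre-dose samples before infusion 2 and Cycle 2 Day 1 are clean values at about 168 h from the start. AUC0-tau is defined over one dosing interval, so a 170-hour sample lies outside it, and a value at the end of a new infusion is not a terminal point of the previous dose. A competent analyst would use the pre-dose sample and drop the later one. This stands as an argument about severity. It does not remove the point, because the plan neither names the pre-dose sample as the end of the profile nor says what to do with the later one.

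A reader might infer that half-life and AUC to infinity cannot be computed, or that neither reading gives a usable profile. The documents do not support either. The planned pre-dose samples allow both calculations, and the start-based reading works apart from one redundant sample.

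Three further limits are fair. The exact clash needs the next infusion to start on time; section 7.2.4.1 allows for delays, and section 7.5 requires committee review before the next cycle, although on-time weekly dosing is the planned case. On Day 8 the literal 168-hour draw would coincide with the separately listed sample after infusion 2, so a site may notice. Finally, PK results are descriptive and untested, and both dose escalation and the MTD rest on DLT counts.

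**Conclusion.** The point holds as a contradiction with an avoidable consequence. That 9.1 and footnote 13 disagree, and that 9.1 puts the 168-hour sample at the end of an on-time next infusion, follows from the documents alone.

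The AUC errors of about 27–45% after infusion 1 and 11–36% after infusion 4, with a rising terminal slope, apply only if the post-dose value is taken as the last point of the profile. They rest on a one-compartment model and an assumed half-life of 3 to 14 days. The size depends on that assumption; the upward direction held in every case run. If the planned pre-dose value replaces it, AUC is within about 2% and half-life is recovered.

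The correction should be made because it concerns listed secondary endpoints, but it does not touch the primary objective.

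**What to change.** 1. State one time origin, in identical words, in the synopsis, section 9.1 and footnote 13.
2. Define the 168-hour sample as the pre-dose sample of the next infusion: infusion 2 after infusion 1, and Cycle 2 Day 1 after infusion 4.
3. State in section 9.1 or 11.3.7 that any sample drawn after the next infusion has started is excluded from AUC0-tau and from the terminal-slope regression, and that actual sampling times are used.
4. If times run from the start of infusion, remove the 2-hour sample as a duplicate of the end-of-infusion sample; otherwise express the early times as hours after the end of infusion.

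The cost is wording in three places plus one analysis rule. No extra samples are needed.

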### **9.2. Pharmacodynamic study**

This study also incorporates mandatory pharmacodynamic study by examining serum concentrations of VEGF-A, soluble VEGFR-1, soluble VEGFR-2. The sampling time points are pre-dose and after each infusion in cycle 1 in conjunction with pharmacokinetic studies.

## 10. ADVERSE EVENT REPORTING

### 10.1. Definitions of an adverse event and causality analysis

An adverse event (AE) is defined as any untoward medical occurrence in a patient or clinical investigation patient administered a pharmaceutical product and which does not necessarily have a causal relationship with this treatment. An adverse event can therefore be any unfavorable and unintended sign (including an abnormal laboratory finding), symptom, or disease temporally associated with the use of a medicinal (investigational) product, whether or not the event is considered causally related to the use of the product.

Each adverse event is to be reported on an Adverse Event CRF page. Adverse events are graded using the Cancer Therapy Evaluation Program (CTEP) CTCAE, Version 4.0 in this study.

If CTCAE grading does not exist for an adverse event, the severity of mild (1), moderate (2), severe (3), life-threatening (4), and death related to an adverse event (5) will be used. Information about all adverse events, whether volunteered by the patient, discovered by Investigator questioning, or detected through physical examination, laboratory testing, or other means, will be collected and recorded on the Adverse Event CRF page and followed as appropriate.

Adverse event monitoring should be continued until adverse event resolution/stabilization (whichever is later).

Medical conditions/diseases present before the infusion of study drug are only considered adverse events if they worsen after receiving any study drug. Clinical events occurring before the administration of study drug but after signing the ICF are to be recorded on the Medical History/Current Medical Conditions CRF page. All laboratory values are to be reviewed by the Investigator and abnormal values will be graded according to CTCAE Version 4 and reported in the study report.

A laboratory abnormality is considered an adverse event if it results in any one of the following:

- discontinuation from study drug,
- necessitates therapeutic medical intervention,
- if the Investigator assesses the abnormality as an adverse event, or
- any laboratory test that is clinically significant or meets the definition of an SAE

It is expected that wherever possible, the clinical, rather than the laboratory term would be used by the reporting investigator (e.g. anemia versus low hemoglobin value). These adverse events

will be recorded on the Adverse Events CRF page and will include all signs, symptoms, or diagnosis associated with them.

The following is required for the description of each adverse event:

Description

Duration (start and end dates)

CTCAE Grade 1 through 5 or severity if CTCAE is not available

Relationship to the study drug - related or not related

Action(s) taken with study drug

Whether event was serious

Whether event is ongoing

## **10.2. Adverse event collection period**

All protocol-related serious adverse events must be collected from the signing of the study specific informed consent until study drug administration.

All serious and non-serious adverse events reported from the time of study drug administration until 28 days following last infusion of study drug administration will be collected, whether elicited or spontaneously reported by the patient.

Serious adverse events occurring after the study-specific informed consent is signed but prior to the first dose of the investigational product will be collected only if they are considered by the investigator to be causally related to the study required procedures.

## **10.3. Relationship to study drug**

The following is used to assess the relationship of the AE to the use of study results. Assessments are to be recorded on the appropriate CRF page.

Causality	Description
Probably Related	An adverse event has a strong temporal relationship to study drug or recurs on re-challenge and another cause of event is unlikely or significantly less likely.
Possibly Related	An adverse event has a strong temporal relationship to the study drug and another cause of event is

Causality	Description
	equally or less likely compared to the potential relationship to study drug.
Probably Not Related	An adverse event has little or no temporal relationship to the study drug and/or a more likely Other cause of event exists.
Not Related	An adverse event is due to an underlying or concurrent illness or effect of another drug and is not related to the study drug (e.g., has no temporal relationship to study drug or has a much more likely Other cause of event).

For causality assessments, events meeting the categories of probably or possibly will be considered "associated." Events that are probably not or not related will be considered "not associated." In addition, when the investigator has not reported causality or deemed it not assessable, it will consider the event associated.

